Select adverse events with potential immune-related causality, previously termed “immune related adverse events” or “adverse events of special interest” were also analyzed taking into account multiple events, with rates adjusted for treatment duration. Most events occurred within the first 6 months of therapy; cumulative or novel toxicities were not observed with prolonged drug exposure. Nineteen of 306 patients (6%) experienced grade 3-4 treatment related select adverse events. Fifty-two of 230 patients (23%) with drug-related adverse events required management with systemic glucocorticoids and/or other immunosuppressive agents. Twenty-one of 52 (40%) resumed nivolumab therapy after toxicity resolved, while others discontinued therapy.

Although tumor progression was the most common cause of mortality, there were 3 drug-related deaths associated with grade 3-4 pneumonitis. Pneumonitis (any grade) occurred in 12 of 306 patients (4%), and grade 3-4 pneumonitis occurred in 4 patients (1%), with clinical presentations ranging from asymptomatic radiographic abnormalities to progressive, diffuse pulmonary infiltrates associated with cough, fever, and/or dyspnea. No clear relationship between

the occurrence of pneumonitis and tumor type, dose level, or treatment duration was noted. In 9 of 12 patients, pneumonitis was reversible with treatment discontinuation and/or immunosuppression (glucocorticoids, infliximab, mycophenolate). There were no pneumonitis associated deaths between November 2011 and March 2013, the point of data analysis, while 79 patients continued to receive nivolumab during this time (median 29 weeks, range 2-69 weeks).

In CA209032 study, Nivolumab monotherapy has been administered to subjects with heavily pre-treated advanced GC, GEJ and EAC. As of Nov 2015, 59 subjects received nivolumab 3 mg/kg every 2 weeks. Nivolumab related AEs of any grade occurred in 70% of subjects (41/59), most of them were grade 1 and 2. Grade 3 - 4 drug related AEs were observed in 17% of subjects (10/59), and no grade 5 drug related events. The safety profile in patients with advanced GC including GEJ and EAC is considered tolerable and manageable similar with other tumor types.¹⁷

Additional details on the safety profile of nivolumab, including results from other clinical studies, are also available in the nivolumab IB.

1.4.7 *Rationale for CA209577 Study Design*

[figure not shown]

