7 STATISTICAL ANALYSES

7.1 General Methods

Unless otherwise noted, discrete variables will be tabulated by the frequency and proportion of subjects falling into each category, grouped by treatment. Percentages given in these tables will be rounded to the first decimal and, therefore, may not always sum to 100%. Percentages less than 0.1 will be indicated as ‘< 0.1’. Continuous variables will be summarized by treatment group using the mean, standard deviation, median, minimum, and maximum values.

Time-to-event variables (e.g. time-to resolution) will be analyzed using the Kaplan-Meier technique. When specified, the median will be reported along with 95% CI using Brookmeyer and Crowley method¹² (using log-log transformation for constructing the confidence intervals¹³).

The conventions to be used for imputing missing and partial dates for analyses requiring dates are described in [Section 8](#).

7.1.1 Adverse Events, Serious Adverse Events, Multiple events, Select Adverse Events, Other Events of Special Interest and Immune-Mediated Adverse Events

Drug-related AEs are those events with relationship to study drug “Related”, as recorded on the CRF. If the relationship to study drug is missing, the AE will be considered as drug-related.

Serious adverse events consist of AEs deemed serious by the Investigator and flagged accordingly in the CRF and clinical database.

Adverse events leading to study drug discontinuation are AEs with action taken regarding study drug(s) = “Drug was discontinued”.

Adverse events leading to dose delay are AEs with action taken regarding study drug(s) = “Drug was delayed”.

Adverse events leading to dose reduction are AEs with action taken regarding study drug(s) = “Dose was reduced”.

Adverse events will be coded using the Medical Dictionary for Regulatory Activities (MedDRA), and the most recent version of the dictionary at the time of the database lock will be used. Adverse event results will be graded for severity using the NCI Common Terminology Criteria for Adverse Events (CTCAE) and the version of the criteria specified in the protocol will be used.

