7.6.6.3 Time-to Resolution of Select AE

Time-to resolution of the following specific events will be summarized separately for each category/subcategory.

- Time-to resolution of drug-related select AE (any grade, grade 3-5) by treatment group
- Time-to resolution of drug-related select AE (any grade, grade 3-5) where immune modulating medication was initiated, by treatment group

Time-to resolution analyses are restricted to treated subjects who experienced the specific events. Time-to resolution where immune modulating medication was initiated analyses are restricted to treated subjects who experienced the specific events and who received immune modulating medication during the longest select AE.

The analyses will be conducted using the 30-day safety window.

The following summary statistics will be reported: percentage of subjects with resolution of the longest select AE, median time-to resolution along with 95% CI (derived from Kaplan-Meier estimation) and ranges.

See time-to resolution definition subsection of [APPENDIX 1](#) for additional details.

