- For other partial/missing dates, the following conventions were used:
 - If only the day of the month is missing, the 15th of the month will be used to replace the missing day.
 - If both the day and the month are missing, “July 1” will be used to replace the missing information.
 - If a date is completely missing, it will be considered as missing.

The following conversion factors will be used to convert days to months or years:

$$1 \text{ month} = 30.4375 \text{ days and } 1 \text{ year} = 365.25 \text{ days.}$$

Duration (e.g. time-to onset, time-to resolution) will be calculated as follows:

$$\text{Duration} = (\text{Last date} - \text{first date} + 1)$$

Last known alive date will be defined based on all appropriate dates collected on the CRF.

All statistical analyses will be carried out using SAS (Statistical Analysis System software, SAS Institute, North Carolina, USA) unless otherwise noted.

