Time-to onset of drug-related AE (any grade or grade 3-5) for a specific category is defined similarly but restricted to drug-related AE.

Time-to onset for a specific subcategory is defined similarly but restricted to event of this subcategory.

Time-to resolution definition

In order to derive the time-to resolution, overlapping or contiguous AEs within a specific category or subcategory will be collapsed into what will be termed “clustered” AEs. For example, if a subject (without pre-treatment AE) experienced an AE from 1st to 5th January, another AE (with different PT but within same category) from 6th to 11th January and same AE from 10th to 12th January, these will be collapsed into one clustered AE from 1st to 12th January. [Table 9-2](#) is summarizing key derivation steps for each type of clustered AEs.

Time-to resolution of AE (any grade) for a specific category is defined as the longest time from onset to complete resolution or improvement to the grade at baseline among all clustered AEs experienced by the subject in this category per adverse event criteria category. Events which worsened into grade 5 events (death) or have a resolution date equal to the date of death are considered unresolved. If a clustered AE is considered as unresolved, the resolution date will be censored to the last known alive date. Improvement to the grade at baseline implies that all different events in the clustered adverse event should at least have improved to the corresponding (i.e. with same preferred term) baseline grade. This measure is defined only for subjects who experienced at least one AE in the specific category.

The time-to resolution of AE (grade 3-5) for a specific category is defined similarly with an onset date corresponding to a grade 3-5 AE.

Time-to resolution of drug-related AE (any grade or grade 3-5) for a specific category is defined similarly but restricted to drug-related AE.

The time-to resolution of AE (any grade or grade 3-5, drug-related or all) where immune modulating medication was initiated is defined similarly. For data presentation not restricted to IMAE, the additional condition that the subject started an immune modulating medication during the longest AE resolution period will be applied.

Time-to resolution for a specific subcategory is defined similarly but restricted to event of this subcategory.

Table 9-2: Derivation of clustered AE

Type of clustered AE	Derivation

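### Time to AE resolution: subjects who die with the event unresolved are censored in a Kaplan-Meier analysis, so the reported median can be too short and is never too long

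*SAP*

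**What the plan says.** SAP 7.1 sets the general method: "Time-to-event variables (e.g. time-to resolution) will be analyzed using the Kaplan-Meier technique". For select AEs, SAP 7.6.6.3 reports the "percentage of subjects with resolution of the longest select AE", followed by the "median time-to resolution along with 95% CI (derived from Kaplan-Meier estimation) and ranges". The event sets include fatal events: "Time-to resolution of drug-related select AE (any grade, grade 3-5) by treatment group".

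Appendix 1 (time-to resolution definition) decides who counts as resolved: "Events which worsened into grade 5 events (death) or have a resolution date equal to the date of death are considered unresolved". The next sentence fixes the censoring: "If a clustered AE is considered as unresolved, the resolution date will be censored to the last known alive date". Section 8 says of that date only: "Last known alive date will be defined based on all appropriate dates collected on the CRF".

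The title of Appendix 1 covers select AEs, immune-mediated AEs (IMAEs) and events of special interest. Section 7.6.7 asks for summaries of time to resolution of endocrine and non-endocrine IMAEs, so the same rule applies there. Unlike 7.6.6.3, section 7.6.7 does not list the percentage resolved. No visible section gives a competing-risk rule for these analyses.

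**The concern.** The rule handles two kinds of subject alike: one alive with an ongoing event, who may still resolve, and one who has died, who cannot. Censoring is right for the first. For the second, Kaplan-Meier removes the subject from the risk set and in effect assumes resolution at the rate seen in those still followed. The resulting curve estimates how fast events would resolve if nobody died, which is not the question a reader brings to a reversibility table.

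The error runs one way: toxicity looks more quickly reversible than it was. It should be largest where deaths with an unresolved event are a sizeable share of a small category, such as grade 3-5 pulmonary events, or where resolution is so slow that deaths from any cause accumulate first. What is at stake is a descriptive safety statistic.

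**Working it through.** **No planned figure to reproduce.** The documents state no expected median time to resolution and no expected number of deaths with an unresolved AE. The steps below show the direction first, then the size over a range of assumptions.

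**1. Direction.** Let λ(u) be the hazard of resolution, R(t) = exp(−∫λ) and D(t) the probability of not having died with the event unresolved.
- Planned estimator: 1−KM estimates ∫λ(u)R(u)du = 1−R(t).
- Cumulative incidence of resolution: ∫λ(u)R(u)D(u)du.

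Since D ≤ 1, the cumulative incidence never exceeds 1−KM, so the KM median is equal or earlier.

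**2. Size under constant hazards.** Let π be the share of subjects with the AE who die unresolved (assumed; not in the documents).
- KM median = ln2/λ.
- Cumulative-incidence median = −(1−π)·ln(1−0.5/(1−π))/λ, which does not exist for π ≥ 0.5.

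At π = 0.25 the second is 0.75 × ln 3 = 0.824/λ, against 0.693/λ. The ratio is 1.189, so KM is 1−1/1.189 = 15.9% too short.

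| π | Ratio of medians | KM too short by |
|---|---|---|
| 0% | 1.000 | 0% |
| 2% | 1.009 | 0.9% |
| 5% | 1.024 | 2.4% |
| 10% | 1.053 | 5.0% |
| 25% | 1.189 | 15.9% |
| 40% | 1.551 | 35.5% |
| ≥ 50% | not reached | KM still gives a finite median |

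**3. A small-sample illustration.** Protocol 1.4.6 describes an earlier phase 1 study with 12 pneumonitis cases and 3 drug-related deaths associated with grade 3-4 pneumonitis: "In 9 of 12 patients, pneumonitis was reversible with treatment discontinuation and/or immunosuppression". Assume the 3 deaths were the 3 cases not reversed, and take the median as the first time the curve reaches 50%.
- The cumulative-incidence median is the 6th resolution of 12.
- Of the 220 possible orderings of 9 resolutions and 3 deaths, the KM median is also the 6th resolution in 188 (85%). It is the 5th in 32 (15%), those with early deaths.

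The same section gives 4 grade 3-4 cases. If 3 died and the fourth resolved (assumed), only 1 of 4 ever resolves and no median exists. KM still reports a finite median in 2 of the 4 orderings: when the resolution comes third (the curve just touches 50%) and when it comes last.

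**4. Slow and fast events.** The death hazards are from SAP Table 5.1-2. They are monthly: exp(−0.026 × 4) = 90.1%, the table's 4-month rate. For nivolumab they are 0.026 to month 4, 0.018 to 1 year, 0.014 to 2.5 years and 0.012 to 6 years. The resolution hazards are assumed, and the clock is started at AE onset although the table runs from randomization.

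| Resolution hazard per month | KM median (months) | Cumulative-incidence median, nivolumab | Same, placebo hazards |
|---|---|---|---|
| 0.03 | 23.1 | 34.5 | 42.1 |
| 0.10 | 6.9 | 7.8 | 7.9 |
| 0.30 | 2.3 | 2.4 | 2.4 |

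**The case against.** The strongest reply is that the SAP does not hide these deaths. For select AEs, 7.6.6.3 puts the percentage resolved in the same set of statistics as the median, and a death counts as not resolved there; in the 12-case example it would be 9/12 = 75%. Sections 7.6.6.1 and 7.6.7 tabulate grade 5 events by category, and 7.6.1 tabulates deaths. This stands, and it limits the harm. It does not correct the median. The percentage does not separate the dead from the living with ongoing events, and 7.6.7 does not list it for IMAEs.

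Several stronger conclusions are tempting and are not supported:
- *The median is always understated.* It is not. Deaths after the median leave it unchanged, and the 12-case example moves in only 15% of orderings.
- *The final or 24-month resolution probability is inflated.* The Kaplan-Meier complement would be, but 7.6.6.3 plans neither figure.
- *The arms cannot be compared.* At 0.10 per month or faster, the two arms' cumulative-incidence medians differ by about 0.1 month or less. A wide gap needs very slow assumed resolution, and no test is planned.
- *The pneumonitis figures predict this trial.* They come from patients with recurrent or treatment-refractory malignancies, not resected, disease-free subjects. Protocol 1.4.6 does not say the deaths were the cases not reversed. It reports no pneumonitis-associated deaths from November 2011 to March 2013, and no drug-related grade 5 events in 59 subjects with gastric, GEJ or esophageal cancer. With no deaths while an event is unresolved, the error is zero.

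**Conclusion.** The concern holds as a minor one. Under the stated rule, the Kaplan-Meier median time to resolution can be too short and is never too long.

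Its size in this trial cannot be derived from the documents. Under constant hazards it is about 2% or less if up to 5% of subjects with the AE die unresolved, and about 16% at 25%. In small categories with high fatality, a finite median can be reported when fewer than half ever resolve. For very slow-resolving events the error could be larger (23 against 34 months at an assumed 0.03 per month); for fast ones it is negligible. All of these rest on assumed death shares or resolution hazards.

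The analysis is descriptive, with no alpha attached. DFS, OS, sample size and the interim boundaries are untouched. Censoring living subjects with ongoing events is appropriate and should stay.

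**What to change.** In Appendix 1, split the censoring sentence: a subject who dies with the clustered AE unresolved has a competing event at the date of death, and only subjects alive with an unresolved AE are censored at the last known alive date.

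In 7.6.6.3 and 7.6.7, estimate the cumulative incidence of resolution by Aalen-Johansen, take the median as the time that curve reaches 50% (report it as not reached otherwise), and show the number who died unresolved by category and arm.

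The cost is SAP wording and a competing-risk code on the existing variable; death dates are already collected. The downside is that some medians will become longer or not reached, and they will differ from summaries made with the current method.

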6.2.1 Nonserious Adverse Event Collection and Reporting

The collection of nonserious AE information should begin at initiation of study drug. Nonserious AE information should also be collected from the start of a placebo lead-in period or other observational period intended to establish a baseline status for the subjects.

All nonserious adverse events (not only those deemed to be treatment-related) should be collected continuously during the treatment period and for a minimum of 100 days following discontinuation of study treatment. Nonserious AEs should be followed to resolution or stabilization, or reported as SAEs if they become serious (see [Section 6.1.1](#)). Follow-up is also required for nonserious AEs that cause interruption or discontinuation of study drug and for those present at the end of study treatment as appropriate. All identified nonserious AEs must be recorded and described on the nonserious AE page of the CRF (paper or electronic).

Completion of supplemental CRFs may be requested for AEs and/or laboratory abnormalities that are reported/identified during the course of the study.

Every adverse event must be assessed by the investigator with regard to whether it is considered immune-mediated. Immune-mediated adverse events (IMAEs) are AEs consistent with an immune-mediated mechanism or immune-mediated component for which non-inflammatory etiologies (eg, infection or tumor progression) have been ruled out. IMAEs can include events with an alternate etiology that were exacerbated by the induction of autoimmunity. Information supporting the assessment will be collected on the subject's case report form.

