 - On-treatment AEs will be defined as AEs with an onset date and time on or after the date and time of the first dose of study treatment (or with an onset date on or after the day of first dose of study treatment if time is not collected or is missing). For subjects who are off study treatment, AEs will be included if event occurred within a safety window of 30 days (or 100 days depending on the analysis) after the last dose of study treatment. No “subtracting rule” will be applied when an AE occurs both pre-treatment and post-treatment with the same preferred term and grade.
 - On-treatment evaluations (laboratory tests, and vital signs) will be defined as evaluations taken after the day (and time, if collected and not missing) of first dose of study treatment. For subjects who are off study treatment, evaluations should be within a safety window of 30 days (or 100 days depending on the analysis) after the last dose of study treatment.

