7.6.7 Immune-Mediated Adverse Events (US Submission)

IMAEs will be summarized by treatment group for each immune-mediated category / PT using the 100-day safety window:

- Overall summary of non-endocrine IMAEs by worst CTC grade (any grade, grade 3-4, grade 5) where immune modulating medication was initiated presented by Category / PT.
- Overall summary of endocrine IMAEs by worst CTC grade (any grade, grade 3-4, grade 5) presented by Category / PT.
- Overall summary of non-endocrine IMAEs leading to discontinuation by worst CTC grade (any grade, grade 3-4, grade 5) where immune modulating medication was initiated presented by Category / PT.

- Overall summary of endocrine IMAEs leading to discontinuation by worst CTC grade (any grade, grade 3-4, grade 5) presented by Category / PT.
- Overall summary of non-endocrine IMAEs leading to dose delay or reduction by worst CTC grade (any grade, grade 3-4, grade 5) where immune modulating medication was initiated presented by Category / PT
- Overall summary of endocrine IMAEs leading to dose delay or reduction by worst CTC grade (any grade, grade 3-4, grade 5) presented by Category / PT.
- Summaries of time-to onset and time-to resolution of non-endocrine IMAEs where immune modulating medication was initiated presented by Category.
- Summaries of time-to onset and time-to resolution of endocrine IMAEs presented by Category.

A by-subject listing of IMAEs will be provided. By-subject listings of time-to resolution for longest IMAEs cluster (any grade and grade 3-5 in separate summaries) will also be provided. For new studies which collect investigator assessment of potential IMAE data, a by-subject listing of AEs considered as immune-mediated events per investigator but not qualified for IMAEs definition will also be provided.

In addition, for all treated subjects who experienced at least one IMAE, the following data presentation will be provided:

- Summary of subjects who were re-challenged with nivolumab by IMAE category, with extended follow-up

For these, re-challenge is considered to have occurred when last nivolumab infusion was administered after the onset of an IMAE.

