Any grade	Collapse any on-treatment AE from the same category
Drug-related of any grade	Collapse any on-treatment drug-related AE from the same category
Grade 3-5	Collapse any on-treatment AE from the same category. Resolution will be based on the onset date of the earliest grade 3-5 records (if no grade 3-5 record, clustered AE is excluded)
Drug-related of Grade 3-5	Collapse any on-treatment drug-related AE from the same category Resolution will be based on the onset date of the earliest grade 3-5 record (if no Grade 3-5 record, clustered AE is excluded)

The algorithm for collapsing adverse event records is using the following conventions:

For each subject and specified category, the corresponding adverse event records will be collapsed when:

- 1) Multiple adverse event records have the same onset date.
- 2) The onset date of an event record is either the same day or 1 day later than the resolution date of a preceding event record (contiguous events).
- 3) The onset date of an event record is after the onset date and prior to or on the resolution date of a preceding event record (overlapping events).

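### Read as written, the time-to-resolution clusters drop continuation records that start after the safety window, so some continuing AEs can be scored as resolved (minor)

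*SAP*

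**What the plan says.** SAP Appendix 1 collapses overlapping or contiguous AE records in a category into one clustered AE. Time to resolution is the subject's longest cluster, measured from onset to full resolution or return to baseline grade. Unresolved clusters are censored at the last known alive date. Two situations are expressly unresolved: worsening to Grade 5, and a resolution date equal to the date of death.

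Table 9-2 says which records enter a cluster. The any-grade row reads "Collapse any on-treatment AE from the same category" and the drug-related row reads "Collapse any on-treatment drug-related AE from the same category". The two Grade 3-5 rows carry the same on-treatment restriction. A record is contiguous when its onset is "either the same day or 1 day later than the resolution date of a preceding event record".

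SAP 6.1 supplies the meaning of on-treatment. It starts from onset: "On-treatment AEs will be defined as AEs with an onset date and time on or after the date and time of the first dose". For subjects off treatment, "AEs will be included if event occurred within a safety window of 30 days (or 100 days depending on the analysis".

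For select AEs, SAP 7.6.6.3 says: "The analyses will be conducted using the 30-day safety window". For IMAEs, whose summaries include time to resolution, SAP 7.6.7 says: "IMAEs will be summarized by treatment group for each immune-mediated category / PT using the 100-day safety window".

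Protocol 6.2.1 collects nonserious AEs for at least 100 days after treatment stops and adds: "Nonserious AEs should be followed to resolution or stabilization".

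**The concern.** The safety window is there to decide which AEs count as on-treatment. Because Table 9-2 applies it to each record that goes into a cluster, it also decides where a qualifying episode ends. Suppose an AE starts inside the window and continues as a new record that starts after it, for example at a new grade or under another preferred term in the same category. The second record is excluded. The cluster then closes at the first record's resolution date, a term that the contiguity rule uses even when another record follows within a day.

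This works against the purpose of collapsing, which is to keep one continuing episode from being scored as several short ones. At stake are the two main outputs of SAP 7.6.6.3, the percentage of subjects whose longest select AE resolved and the median time to resolution. The error runs one way: percentage too high, time too short. Closing a cluster early can also change which cluster is a subject's longest, and whether immune-modulating medication started during it.

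**Working it through.** **1. The SAP's own example.** Appendix 1 gives records on 1-5, 6-11 and 10-12 January and collapses them into one cluster, 1-12 January. Applying the three collapsing rules with duration = last date - first date + 1 (SAP 8) reproduces this: 12 - 1 + 1 = 12 days.

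**2. The same example with the window applied first.** Assume the window closes on 5 January. The second and third records start on 6 and 10 January and are excluded. The cluster becomes 1-5 January, resolved, 5 days. If linked records are kept, it remains 12 days.

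**3. Assumed subjects, with days counted from the last dose.**

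| Records | Window | As written | Linked |
|---|---|---|---|
| Days 20-34, then 35-80 | 30 | 15 days, resolved | 61 days, resolved |
| Days 20-34, then 35 ongoing, last known alive day 200 | 30 | 15 days, resolved | unresolved, censored at 181 days |
| Days 20-34, then 35-80 | 100 | 61 days, resolved | 61 days, resolved |
| Days 90-104, then 105 ongoing, last known alive day 200 | 100 | 15 days, resolved | unresolved, censored at 111 days |
| One record, days 20-80 | 30 | 61 days, resolved | 61 days, resolved |

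The break needs at least two records, with the later one starting after the window. One long record keeps its true end date.

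**4. How often, under assumptions.** The documents give no record counts or durations. Assume that every episode has two contiguous records and that the first is exponential with mean m. A cluster is cut when onset plus first-record length exceeds the window W.

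- Onset uniform over 365 days of treatment plus 30 days, W = 30: share cut ≈ m/395. For m = 14, 14/395 = 3.5%. For m = 28, 28/395 = 7.1%. If only one third of episodes had a continuation record (assumption), these become about 1.2% and 2.4%.
- Onset uniform over the dosing interval D after the last dose: share cut = (m/D) × [exp(-(W - D)/m) - exp(-W/m)].

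| W | D | m = 14 | m = 28 |
|---|---|---|---|
| 30 | 14 | exp(-16/14) - exp(-30/14) = 20% | 2 × [exp(-16/28) - exp(-30/28)] = 44% |
| 30 | 28 | 0.5 × [exp(-2/14) - exp(-30/14)] = 37.5% | exp(-2/28) - exp(-30/28) = 59% |
| 100 | 14 | 0.1% | 3.6% |
| 100 | 28 | 0.2% | 4.8% |

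With m = 7 and W = 30 the share is 4% (D = 14) or 18% (D = 28).

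- Effect on the median in these late-starting two-record episodes, W = 30 and second-record mean 56 days (simulation): for m = 14, from 54 days to 41 (D = 14) or 32 (D = 28); for m = 28, from 69 to 45 or 38.

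The 0 to 5% at 100 days is for AEs that start within one dosing interval of the last dose. An AE that starts close to day 100 is exposed in the same way as one close to day 30 under the shorter window.

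**The case against.** The strongest reply is that Appendix 1's definition governs and Table 9-2 only summarises derivation steps. A Grade 3 record closed because the event became Grade 1 is neither fully resolved nor, in general, back at baseline, so calling it resolved contradicts the definition. The upper limit in SAP 6.1 also speaks of the event occurring in the window, so a later grade-change record might be read as part of an AE that began inside it. Both readings are possible, but the SAP instructs neither. The baseline-grade check covers only events inside the cluster, and continuation after the window is not among the listed unresolved cases. What stands is that this is a gap between the table and the definition, not an explicit instruction to miscount.

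A reader might infer that a Grade 5 record starting after the window would leave the episode scored as resolved. The documents do not support that firmly. The sentence treating events that worsen to Grade 5 as unresolved is not limited to in-window records and can be read as covering this case.

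It is also fair that the documents do not show that each grade change creates a new record, and that SAP 7.1.1 leaves some record processing to cited sponsor algorithms that are not available here. The Appendix 1 example does, however, contain contiguous records in one category with different preferred terms, so multi-record episodes are expected. By-subject listings of select AEs and of IMAE resolution times partly mitigate the problem.

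**Conclusion.** The point holds as a minor one. For subjects off treatment, Table 9-2 read with SAP 6.1 can close a continuing episode at day 30 (select AEs) or day 100 (IMAEs) when the continuation is a new record. The direction is certain: more clusters resolved, and sooner. The size is not. About 3.5 to 7% of clusters at 30 days assumes two records in every episode, a mean first record of 14 to 28 days and onset spread evenly over a year plus 30 days. It falls in proportion if fewer episodes have a continuation record. Even onset is itself doubtful, since Protocol 1.4.6 reports for another nivolumab study that most select AEs came in the first 6 months.

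Two stronger readings are tempting. One is that 20 to 59% of the reported clusters are affected; that range covers only assumed two-record AEs starting in the dosing interval after the last dose. The other is that the nivolumab arm's toxicity will look more reversible than the data show; the documents hold no trial results by arm, so a difference between arms is inference. The analysis is descriptive safety and leaves DFS and OS untouched.

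**What to change.** In SAP Appendix 1, Table 9-2, use the safety window only to select clusters: a cluster qualifies if at least one record of the type that the row requires has an on-treatment onset. Then extend it with later contiguous or overlapping records of that same type, whatever their onset, and take resolution from the end of the extended cluster. Same type means the same category and, in the drug-related rows, drug-related records only. Without that limit, unrelated events could lengthen drug-related clusters, which Appendix 1 restricts to drug-related AEs. State also that a linked Grade 5 record makes the cluster unresolved.

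The cost is a sentence or two and a small programming change. Later records should already be in the database, given the follow-up that Protocol 6.2.1 requires. The reported figures become slightly less favourable, and some late records may fall after subsequent therapy has started, which the report should note.
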